7.5 Pooling Strategy for Study Sites

Generally, the data of all study sites will be analyzed together. The logistic regression model for the efficacy analysis will use study site as a factor. In the case of study sites

with fewer than 5 subjects, those study sites may be combined into entities of similar size for the purpose of including in the logistic regression model as a factor.

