9.4.2 Primary Efficacy Endpoint

The primary efficacy endpoint is the proportion of patients who have neither of the following:

- Intra-operative CSF leakage from dural repair after up to two FS VH S/D 500 s-apr/control applications during Valsalva manoeuvre (25 cm H₂O for up to 5 - 10 seconds)
- Post-operative CSF leakage within 30 (+3) days post-operatively

The specific hypotheses of the proportion difference to be tested are as follows:

$$H_0: P_{FS} - P_{DS} \leq -0.10$$

$H_a: P_{FS} - P_{DS} > -0.10$

where

P_{FS} = the proportion of patients not meeting the 2 criteria (ie, no intra-operative CSF leakage and no post-operative CSF leakage) for the FS VH S/D 500 s-apr treatment group, and

P_{DS} = the proportion of patients not meeting the 2 criteria (ie, no intra-operative CSF leakage and no post-operative CSF leakage) for the DuraSeal Dural Sealant treatment group.

The primary composite efficacy endpoint, proportion of patients not meeting the 2 criteria (ie, no intra-operative CSF leakage and no post-operative CSF leakage), will be investigated by a 2-sided test for non-inferiority using logistic regression, taking into account the following covariates: study center and surgery region. Non-inferiority of FS VH S/D 500 s-apr to DuraSeal Dural Sealant will be assessed using the confidence interval approach and a NI margin of 10%.

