5.3 Sample Size

The number of subjects in a clinical trial should always be large enough to provide a reliable answer to the questions addressed. This number is usually determined by the primary objective of the trial. If the sample size is determined on some other basis, then this should be made clear and justified. For example, a trial sized on the basis of safety questions or requirements or important secondary objectives may need larger numbers of subjects than a trial sized on the basis of the primary efficacy question (see ICH E1A).

This study is designed to show non-inferiority (NI) of FS VH S/D 500 s-apr compared to DuraSeal Dural Sealant based on the primary composite efficacy endpoint. The

proportion of patients meeting the composite primary endpoint is assumed to be █% for FS VH S/D 500 s-apr and █% for DuraSeal. Using a non-inferiority margin of 10% (the largest clinically acceptable difference), a 1-sided Type 1 error rate (α) of 2.5%, a statistical power ($1-\beta$) of 80%, that one interim analysis is performed after 50% of the patients complete the study, the sample size estimation results in 202 evaluable patients. Assuming a group sequential design utilizing O'Brien-Fleming boundaries, the study may be stopped early for futility if a p-value >0.2486 is observed at the interim. The estimation of sample size was performed using SAS 9.4 software (SAS Institute; Cary, NC). The primary analysis will be performed on the per protocol analysis set (PPS). Assuming that the PPS is 10% less than the total number of randomized subjects, 112 patients per treatment group should be randomized, and there will be 224 patients in total.

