7.4 Interim Analysis

An interim analysis will be conducted after the completion of 50% of patients. A group sequential design utilizing O'Brien-Fleming boundaries will be carried out. Basic demographic tables will be produced during the interim analysis. Predicted values for the primary outcome will be produced from a logistic regression equation containing terms for treatment, site and surgical region (supratentorial or posterior fossa). A one-sided two sample t-test will be performed to compare the lower bound of the difference (active – control) between treatments in the mean predicted proportions against the null value of -0.1, to test whether the mean predicted value for Tisseel is less than -0.1 less than the mean predicted value for Duraseal. The study may be stopped early for futility if a p-value >0.2486 is observed. If the study is stopped early, a full analysis of all of the data will be produced.

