10. EFFICACY

10.1 Primary Efficacy Assessment

The primary efficacy analysis will be carried out on the PPS. The analysis using the FAS will be supportive. The primary efficacy endpoint is the proportion of patients who have neither of the following:

- Intra-operative CSF leakage from dural repair after up to two FS VH S/D 500 s-apr/control applications during Valsalva manoeuvre (25 cm H₂O for up to 5 - 10 seconds)
- Post-operative CSF leakage within 30 (+3) days post-operatively

The specific hypotheses of the proportion difference to be tested are as follows:

$$H_0: P_{FS} - P_{DS} \leq -0.10$$

$$H_a: P_{FS} - P_{DS} > -0.10$$

P_{FS} = the proportion of patients not meeting the 2 criteria (ie, no intra-operative CSF leakage and no post-operative CSF leakage) for the FS VH S/D 500 s-apr treatment group, and

P_{DS} = the proportion of patients not meeting the 2 criteria (ie, no intra-operative CSF leakage and no post-operative CSF leakage) for the DuraSeal Dural Sealant treatment group.

The primary composite efficacy endpoint, proportion of patients not meeting the 2 criteria (ie, no intra-operative CSF leakage and no post-operative CSF leakage), will be investigated by a 2-sided test for non-inferiority using logistic regression, taking into account the following covariates: study center and surgery region. The null hypothesis will be tested against the alternative using logistic regression, taking into account the following covariates: study center and surgery region (supratentorial or posterior fossa). The method described in reference 1 will be used: The parameters of the fitted logistic regression model will be used to predict the success rate of all subjects for both Tisseel and Duraseal treatment. The average response rate per group will be calculated as well as the difference between the two rates. The standard error of the difference will be derived using the delta method in order to construct a 95% confidence interval. A non-inferiority margin of 10% (the largest clinically acceptable difference) will be used; thus, if the lower bound of the 2 sided 95% CI (based on normal approximation) around the difference in proportions (Tisseel group – Duraseal group) is greater than -10% in the final analysis, Tisseel will be declared non-inferior to Duraseal.

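### The non-inferiority interval is fitted with individual site terms and no binding limit on their number, so its one-sided error exceeds 2.5%; the site terms matter mainly from about 10 sites upward

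*SAP*

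**What the plan says.** - **Model.** Protocol 9.4.2 tests the primary endpoint "using logistic regression, taking into account the following covariates: study center and surgery region". SAP 7.5 is explicit that centre means the individual site: "The logistic regression model for the efficacy analysis will use study site as a factor".
- **Pooling.** For sites with fewer than 5 patients, SAP 7.5 says "those study sites may be combined into entities of similar size". This is permissive, names no groups and sets no upper limit on the number of levels.
- **Interval.** SAP 10.1 averages the predictions over all patients under each treatment. It continues: "The standard error of the difference will be derived using the delta method in order to construct a 95% confidence interval". Non-inferiority is declared if "the lower bound of the 2 sided 95% CI (based on normal approximation) around the difference in proportions" lies above -10%.
- **Interim.** SAP 7.4 uses the same terms, "a logistic regression equation containing terms for treatment, site and surgical region (supratentorial or posterior fossa"), and makes the stop optional: "The study may be stopped early for futility if a p-value >0.2486 is observed".
- **Error rate.** SAP 5.3 states "a 1-sided Type 1 error rate (α) of 2.5" percent.
- **Sites.** Protocol 4.1 names four countries and allows more. No site count appears in either document, and neither says what is done with sites that have no failures.

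**The concern.** A normal-approximation interval from a logistic model relies on there being enough events for each fitted parameter. Here each site adds a parameter while the number of failures stays small. Fits with many levels and few events are biased, and sites with no failure are fitted at 100% success and add nothing to the variance. The standard error comes out too small, the lower bound sits too high, and the mistake favours declaring non-inferiority. That bound is the only basis for the trial's confirmatory claim. How far the error departs from 2.5% depends on how many sites recruit and on a discretionary pooling choice, and the plan fixes neither.

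**Working it through.** **Inputs.** Margin 10 points, one-sided 2.5%, 202 evaluable patients, taken as 101 per arm (SAP 5.3). Control success 90.6%, with 85.0% as the lower figure (protocol 9.2.1). Supratentorial to posterior fossa about 3:1 (protocol 4.1). Assumed: 5 to 30 sites, and ordinary maximum likelihood.

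**1. The plan's sample size.** The test-arm rate is redacted, so 202 can only be checked for consistency. The formula is n per arm = (1.960 + 0.842)² × [p_T(1-p_T) + p_C(1-p_C)] / (p_T - p_C + 0.10)². With 90.6% in both arms it gives 134. With 91.8% against 90.6% it gives 7.849 × 0.1604 / 0.01254 = 100.4, so 101. The design therefore fits a test-arm rate near 92%. The type I error check does not need that rate.

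**2. Failures at the null boundary.** 101 × 0.194 + 101 × 0.094 = 29.1. With 30 equal sites, the expected number with no failure is about 30 × (0.806 × 0.906)^(101/30) = 10.4.

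**3. The interval without covariates.** Exact binomial enumeration of the unadjusted Wald rule at 101 per arm gives 2.77%. So about 0.3 points of excess exist before any site term enters.

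**4. The planned analysis, simulated.** Logistic model with treatment, region and site; predictions averaged over all patients; delta-method standard error from the full covariance matrix; non-inferiority declared if the lower bound exceeds -10 points. Equal sites, no pooling, blocks of 4 (assumed), 60,000 trials per row, Monte Carlo SE 0.07-0.08 points:

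| Sites | Planned model | Planned, futility always followed | Region only | Mean model SE / true SD (planned) |
|---|---|---|---|---|
| 5 | 3.11% | 2.84% | 2.95% | 0.97 |
| 10 | 3.14% | 2.85% | 2.85% | 0.96 |
| 15 | 3.36% | 3.00% | 2.87% | 0.95 |
| 20 | 3.61% | 3.21% | 2.90% | 0.93 |
| 30 | 4.02% | 3.52% | 2.92% | 0.91 |

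Simulations with unequal sites, site heterogeneity and either minimisation or random blocks give means of 3.0% at 5 sites, 3.2% at 10, 3.5% at 20 and 4.0% at 30. All runs together, smaller ones included, support about 3.0%, 3.1-3.25%, 3.5-3.7% and 3.5-4.0%. Without site terms the SE ratio is 0.98-1.00.

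**5. Cross-check.** If the standard error is too small by a factor r, the one-sided error is roughly Φ(-1.96 r). For r = 0.98 this is 2.7%, and for r = 0.91 it is 3.7%. Adding the 0.27 points from step 3 gives about 3.0% and 4.0%, as simulated.

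**6. What the plan's own features remove.**
- *Pooling sites under 5:* with 15-30 unequal sites, 3.3-3.7% remains. With 30 equal sites (202/30 = 6.7 patients each) pooling is never triggered.
- *Futility:* if always followed, about 2.7-2.8% at 5 sites rising to 3.5% at 30. This uses a model-based z-statistic in place of the SAP 7.4 t-test.
- *Control rate 85.0% (75.0% vs 85.0%, about 40 failures):* 2.8-2.9% at 5 sites and 3.7-3.8% at 30 unpooled.

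**7. Four country-like levels instead of sites.** 3.03%, 2.98%, 3.14% and 2.94% at 5, 10, 20 and 30 sites (40,000-100,000 trials each). The growth with site count disappears; the Wald excess stays.

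**The case against.** The strongest reply is that the size rests on a site count the documents do not give. At 5 sites the planned model gives 3.07% and four country levels 3.03%, so the change gains nothing; at 10 sites the figures are 3.21% and 2.98%. This stands, and it limits the point to roughly 10 sites or more.

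Second, the SAP already provides for pooling. That stands in part: pooling brings the upper end down to 3.3-3.7%, but it is optional and need not be triggered.

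Third, SAP 10.1 relies on a cited method paper that is not available here, and the documents do not name the fitting method. Maximum likelihood is therefore an assumption, though the natural one for a logistic regression described without qualification.

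Fourth, centre is a stratification factor and belongs in the model. That is a fair principle; it argues for keeping centre in coarse form, not for an unlimited number of levels.

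Three stronger readings are tempting but not supported:
- *The trial runs at 4% error.* That needs about 30 unpooled sites, which no passage states.
- *The delta method ignores uncertainty in the site effects.* It does not; the simulations use the full covariance matrix, site terms included. The shortfall comes from sparse-data bias.
- *The whole excess comes from the site factor, so removing it restores 2.5%.* The Wald form alone gives 2.77%, and about 2.9-3.1% remains after pooling by country.

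**Conclusion.** The concern holds in a bounded form and should be fixed. As written, the plan does not deliver the one-sided 2.5% it states. The Wald interval contributes about 0.3-0.4 points at any site count. Individual site terms add little at 5 sites, but bring the error to about 3.5-3.7% at 20 sites and 3.5-4.0% at 30 unpooled sites, in the direction of declaring non-inferiority. No credit can be taken for the futility stop, because it is optional.

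The result rests on 5-30 sites, maximum-likelihood fitting, and 80.6% vs 90.6% as the null boundary. Confidence is medium: the mechanism and the trend with site count are well reproduced, but where this trial falls on that trend cannot be known from the documents.

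**What to change.** In SAP 7.5, replace the optional combination of small sites with a mandatory rule, fixed before the interim analysis, that limits the levels in the primary model. For example: *For the primary model, study sites will be pooled by country (4 levels); any country added later will be assigned to one of these groups before the interim analysis.*

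Use the same terms in SAP 7.4, SAP 10.1 and protocol 9.4.2. Keep the standardised risk difference, the delta-method interval and the -10% criterion. Report the individual-site model as a sensitivity analysis. State in SAP 5.3, and correspondingly in protocol 9.2, that the one-sided error of this Wald interval is about 2.9-3.1%, not 2.5%.

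**Cost.** Wording only, no new data. Centre, a stratification factor, stays only in coarse form. At an assumed 92% test-arm rate, nominal power falls by about 1-2 points (83.5% to 82.6% on average; 84.3% to 82.5% at 30 sites). If the test-arm rate were 90.6%, the loss reaches 3 points at 30 sites (72.2% to 69.2%). Part of that lost power was never real, since the planned model gains it from a standard error that is too small.

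If the sponsor wants the error at or below 2.5%, a region-stratified score interval gives about 2.4%, but with power of about 77-78%. That is a trade-off for the sponsor and not needed to resolve this point.

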7.6 Visit Windows/Unscheduled Visits

For tabulation, values will be summarized according to the planned time point as recorded in the eCRF. Data recorded at unscheduled visits will only be listed.

7.7 Other Issues

Not applicable.

7.8 Changes to Planned Analyses Described in the Clinical Investigation Plan

Not applicable.

8. DEMOGRAPHICS AND BASELINE CHARACTERISTICS

Demographic and baseline variables as collected in the eCRF will be summarized according to the general principles as detailed above. Demographics will include sex, race, ethnicity, age (years), height (cm), weight (kg) and BMI (kg/m²). Medical history will be coded using MedDRA and incidences will be tabulated by System Organ Class and Preferred Term. Previous medication (stopped before the surgery) and concomitant medication and non-drug therapies (ongoing at the time of surgery or started between surgery and end of study participation) will be coded using WHO Drug Dictionary (medications) and MedDRA (non-drug therapies) and tabulated by ATC Term and Preferred Term.

9. SURGERY DETAILS AND EXPOSURE

The following information on the surgery will be tabulated and/or provided in a listing.

9.1 Planned Surgery Details

- Hospitalization for planned study surgery admission/discharge dates (listing only)
- Duration of hospital stay for planned study surgery (days, to nearest half day)
- Indication for surgery (categories TBD)
- Surgery type [craniotomy with planned durotomy, craniectomy with planned durotomy]
- Surgery region [posterior fossa, supratentorial]

9.2 Intraoperative Details

- Length of sutured durotomy (cm)
 - Needle type used for closure (listing only)
-
- 

- Atraumatic needle
 - Ethicon (atraumatic needle 12 or 17, fibre 5/0, 70 cm)
 - Type E6 / 0.6x16 (surgical needles)
 - TF taper needle
 - RB-1 needle
 - Cylindric
 - Cylindric taper 17mm (HR17)
 - Round bodied
 - CV-23 Taper ½ 17mm; RB-1 plus 17 mm ½
 - Other (specified)
 - Suture material (listing only)
 - Neuolon 4-0 suture
 - Vicril
 - Absorbable (polyglactin)
 - Silk, braided, coated, non-absorbable (polyester)
 - SurgiPro II (Monofilament PP)
 - Ethicon-Ethiban Excel 4.0 PE non-resorbable
 - Other (specified)
 - Suture technique (listing only)
 - Continuous simple
 - Continuous locked
 - Interrupted
 - Other (specified)
 - Tenting sutures used [yes/no] (listing only)
 - Dural material used [yes/no] (listing only)
 - Dural closure method
 - Suture + autologous material
 - Suture + non-autologous material
 - Suture + other material
 - Suture only
 - Type of material used [autologous, non-autologous, other (specified)] (listing only)
 - If type of material used is autologous, specify [fascia, muscle, pericranium]
 - If type of material used is non-autologous, specify [dura patch, hemostasis matrix, other (specified)]
 - Surgery start date/time (first skin cut) (listing only)
-
-

- Primary dura closure date/time (listing only)
- Surgery end date/time (last skin suture) (listing only)
- Duration of surgery (min) (date/time of last skin suture – date/time of first skin cut)
- Duration from dural closure to end of surgery (min) (date/time of last skin suture – primary dura closure date/time)
- Drainage left after surgery
- Any surgical complications
- Actual treatment applied
- Number of study product applications
- Start/stop times of study product application(listing only)
- Volume of treatment applied (mL) (listing only)
- Type of CSF leak [spontaneous, following Valsalva] (listing only)
- If applicable, time of Valsalva maneuver (listing only)
- If applicable, time of watertight closure (listing only)
- If applicable, type of leak [overflow, seepage, weeping, sweating] (listing only)
- Rescue therapy needed

9.3 Rescue Therapy Details (listing only)

- Reason for rescue therapy
- Time of rescue therapy
- Time watertight dura closure achieved
- Actions performed to achieve watertight dura closure
- Brand name of material used to achieve water tight dura closure
- Material type
- Suture technique

9.4 Post-operative Clinical Assessment of CSF Leak

The following information will be tabulated and/or provided in a listing, by date/visit of assessment (Visit 3, 4, 5 or Unscheduled).

- CSF Leak observed
 - Type of CSF leak, if applicable (listing only) Drain duration (days)
 - Output volume (mL)
 - Beta2-transferrin result
 - MRI/CT Done
-
- 

- MRI/CT findings, if applicable (listing only)
- Surgical revision required

9.5 Surgical Revision

- Indication for surgical revision (listing only)
- Procedure description (listing only)
- Start date/time:End date/time (listing only)
- Complications associated with surgical revision

9.6 Surgical Site Infection

The following information will be tabulated and/or provided in a listing, by date/visit of assessment (Visit 3, 4, 5 or Unscheduled).

- Signs of surgical site infection observed
- Type of surgical site infection, if applicable

10. EFFICACY

10.1 Primary Efficacy Assessment

The primary efficacy analysis will be carried out on the PPS. The analysis using the FAS will be supportive. The primary efficacy endpoint is the proportion of patients who have neither of the following:

- Intra-operative CSF leakage from dural repair after up to two FS VH S/D 500 s-apr/control applications during Valsalva manoeuvre (25 cm H₂O for up to 5 - 10 seconds)
- Post-operative CSF leakage within 30 (+3) days post-operatively

The specific hypotheses of the proportion difference to be tested are as follows:

$$H_0: P_{FS} - P_{DS} \leq -0.10$$

$$H_a: P_{FS} - P_{DS} > -0.10$$

P_{FS} = the proportion of patients not meeting the 2 criteria (ie, no intra-operative CSF leakage and no post-operative CSF leakage) for the FS VH S/D 500 s-apr treatment group, and

P_{DS} = the proportion of patients not meeting the 2 criteria (ie, no intra-operative CSF leakage and no post-operative CSF leakage) for the DuraSeal Dural Sealant treatment group.

The primary composite efficacy endpoint, proportion of patients not meeting the 2 criteria (ie, no intra-operative CSF leakage and no post-operative CSF leakage), will be investigated by a 2-sided test for non-inferiority using logistic regression, taking into account the following covariates: study center and surgery region. The null hypothesis will be tested against the alternative using logistic regression, taking into account the following covariates: study center and surgery region (supratentorial or posterior fossa). The method described in reference 1 will be used: The parameters of the fitted logistic regression model will be used to predict the success rate of all subjects for both Tisseel and Duraseal treatment. The average response rate per group will be calculated as well as the difference between the two rates. The standard error of the difference will be derived using the delta method in order to construct a 95% confidence interval. A non-inferiority margin of 10% (the largest clinically acceptable difference) will be used; thus, if the lower bound of the 2 sided 95% CI (based on normal approximation) around the difference in proportions (Tisseel group – Duraseal group) is greater than -10% in the final analysis, Tisseel will be declared non-inferior to Duraseal.

10.2 Secondary Efficacy Assessment

The secondary efficacy endpoints are the following:

- Incidence of intra-operative CSF leakage following final Valsalva manoeuver
- Incidence of CSF leaks within 30 (+3) days post-operatively
- Time in surgery (minutes)
- Time from dural closure (application of IP) until end of surgery
- Length of stay in hospital (days)

The logistic regression approach used for the primary efficacy endpoint will also be used to calculate the proportions of patients with incidence of intra-operative CSF leakage following final Valsalva manoeuver and incidence of CSF leaks within 30 (+3) days post-operatively. The time in surgery, time from dural closure until end of surgery, and the length of stay in hospital will be compared between the 2 groups using a Wilcoxon rank sum test.

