5.4 Randomization Procedure

Patients will be randomly assigned to FS VH S/D 500 s-apr or DuraSeal Dural Sealant at a ratio of 1:1. Randomization will be stratified by study center and surgical region (PF or ST) with the goal of achieving an approximate 3:1 ratio (ST:PF) of the 2 surgical regions in the randomized study population. Randomization will be controlled via an interactive Webresponse system (IWRS), [REDACTED] using dynamic allocation. On the day of surgery (Day 0), upon confirmation of pre-operative eligibility criteria, a member of the site study staff other than the surgeon will obtain a treatment assignment from the IWRS. Adequate amounts of FS VH S/D 500 s-apr and DuraSeal Dural Sealant will be taken into the operating room for potential use as the study treatment.

Immediately after the patient's intra-operative eligibility for study treatment has been confirmed (ie, spontaneous CSF leak or CSF leak after Valsalva maneuver), the assigned treatment will be revealed to the surgeon and the assigned IP or control will be applied to the CSF leak site. Following surgery, the treatment assignment and the actual treatment applied will be entered in the eCRF for the patient. If the patient's eligibility is not confirmed intra-operatively, the operation will be performed according to hospital standards. The study site designee will document the noncompliant criterion or criteria plus the date and reason(s) for the patient's exclusion in the eCRF, and an entry will be made in the IWRS that the study treatment was not administered.

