11. SAFETY

The secondary safety endpoints are the following:

- Incidence of CSF leaks within 60 (+3) days post-operatively
 - Incidence of AEs up to 60 (+3) days post-operatively
 - Incidence of SSIs according to US NHSN within 30 (+3) days post-operatively
-
- 

- Number of unplanned interventions within 30 (+3) days post-operatively
- Laboratory values and vital signs (e.g., elevated WBC count, fever [temperature >100.7°F or 38.2°C], tachycardia [pulse >100], hypotension [mean arterial pressure <60]).

The logistic regression approach used for the primary efficacy endpoint will be used to calculate the proportions of patients with: incidence of CSF leaks within 60 (+3) days post-operatively, and incidence of SSIs according to NHSN within 30 (+3) days postoperatively. The number of unplanned interventions within 30 (+3) days post-operatively will be compared between the 2 treatment groups using a Wilcoxon rank sum test.

The duration and incidence of each laboratory and vital sign abnormality will be recorded. Abnormal laboratory values will be observed, followed, and managed by the investigator for a return to baseline, per standard of care. Clinical laboratory parameters and vital signs will be summarized by visit and treatment group. Absolute values and changes from baseline will be presented. Shift tables for baseline vs. worst post baseline assessment (normal, abnormal/not clinically significant, abnormal/clinically significant) will be generated for laboratory parameters.

An AE overview summary table will be prepared including the number of patients reporting an AE, the percentage of patients (%) with an AE, and the number of events reported, for the following categories:

1. Deaths.
2. SAEs.
3. AEs leading to withdrawal.
4. Severe AEs.
5. Related AEs.
6. AEs of special interest.

Adverse events will be tabulated by body system using the Medical Dictionary for Regulatory Activities (MedDRA). The table will display the total number of patients reporting an AE, the percentage of patients (%) with an AE, and the number of events reported by system organ class (SOC) and preferred term. In addition, tables will be

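### Four secondary comparisons use an unstratified Wilcoxon test despite randomisation stratified by surgical region; the test stays valid but loses power if region predicts these outcomes

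*SAP*

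**What the plan says.** Allocation is 1:1, stratified by study centre and surgical region (posterior fossa, PF, or supratentorial, ST), aiming at roughly three ST patients for each PF patient (Protocol 5.2, SAP 5.4).

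The primary endpoint is analysed by logistic regression "taking into account the following covariates: study center and surgery region" (SAP 10.1). The same approach is used for intra-operative leaks and 30-day leaks (SAP 10.2), and for 60-day leaks and surgical site infections (SAP 11).

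Four comparisons drop both factors:

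- Time in surgery, time from dural closure to end of surgery, and length of stay "will be compared between the 2 groups using a Wilcoxon rank sum test" (SAP 10.2; likewise Protocol 9.4.3).
- The number of unplanned interventions "will be compared between the 2 treatment groups using a Wilcoxon rank sum test" (SAP 11; likewise Protocol 9.4.4).

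Neither document names a stratum, a covariate or a sensitivity analysis for these tests. The site-pooling rule in SAP 7.5 refers only to the logistic model. No alpha, power, success rule or multiplicity scheme is stated for the four comparisons.

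**The concern.** If region is prognostic and treatment is balanced within region, an unstratified rank test leaves the PF-ST difference in the outcome as noise. Two things follow: power falls, and the true rejection rate under the null drops below nominal, because the test's variance ignores the balance that stratification created.

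The documents give some reason to expect a region effect. Protocol 1.1 lists PF surgery as a risk factor for CSF leak and cites leak rates of 6.3% for ST and 12.8% for infratentorial procedures. It also links leaks to meningitis and to surgical site infection, and the latter to longer hospital stay. Management of meningitis and deep infection counts as an unplanned intervention (Protocol 6.12).

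The stake is largest for unplanned interventions, a safety endpoint: lost power there makes a real difference between the sealants harder to see.

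**Working it through.** **The plan's own figure.** SAP 5.3 states that "the sample size estimation results in 202 evaluable patients". With 10% excluded from the per-protocol set, 202/0.9 = 224.4, against 224 stated, so the figures agree. They concern the primary endpoint only; there is no stated power for the Wilcoxon comparisons to reproduce.

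**Inputs.**
- From the documents: N = 202 (101 per arm), 1:1 allocation, ST:PF about 3:1, hence PF fraction p = 0.25 (50 PF, 152 ST).
- Assumed: two-sided 5% level; treatment shift 0.4 SD; PF-ST difference δ from 0 to 1.5 SD; within-region SD 1.

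**Analytic approximation (difference in means, exact balance within region).**
- Share of variance due to region: R² = p(1−p)δ² / [1 + p(1−p)δ²] = 0.1875δ² / (1 + 0.1875δ²).
- True size of the unadjusted test: 2[1 − Φ(1.96/√(1−R²))].
- Power: Φ(0.4/√(4/202) − 1.96/√(1−R²)), where 0.4/√(4/202) = 2.843.
- At δ = 1: R² = 0.1875/1.1875 = 0.158 and 1.96/√0.842 = 2.136. Size is 3.3% and power Φ(0.707) = 76.0%. The adjusted test has power Φ(2.843 − 1.96) = 81.1%.
- At δ = 0.5 and 1.5: size 4.5% and 1.9%; power 79.9% and 69.3%.

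**Simulation of the rank tests.** The van Elteren statistic sums the within-region rank-sum deviations, each weighted by 1/(n_h + 1), and divides by the matching standard error. Results from 5,000 to 6,000 trials per cell with exact balance within region:

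| δ (SD) | Size, plain | Size, by region | Power, plain | Power, by region | Loss (points) |
|---|---|---|---|---|---|
| 0 | 5.5% | 5.3% | 79.3% | 79.5% | 0.2 |
| 0.5 | 4.6% | 4.9% | 77.3% | 78.6% | 1.3 |
| 1.0 | 3.5% | 4.9% | 72.7% | 78.0% | 5.3 |
| 1.5 | 2.2% | 5.1% | 67.0% | 79.0% | 12.0 |

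Monte Carlo error is about 0.3 points on size and 0.5 on power. Across repeated simulations, the plain test's size was about 4.2–4.8%, 3.2–3.5% and 1.8–2.2% at 0.5, 1 and 1.5 SD. Length of stay recorded to the half day behaves alike: at 1 SD, power is 73.6% plain and 78.8% by region.

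**Exclusion after assignment.** Treatment is assigned before intra-operative eligibility is known (Protocol 5.2), and patients who then fail are not counted as randomised (SAP 6.1). As an extreme, suppose every screen failure follows assignment: 476 × 202/224 ≈ 429 assigned, thinned at random to 202. At 0.5, 1 and 1.5 SD:
- Plain size is 5.1%, 4.0% and 3.5% (about 4.4–5.1%, 4.0–4.6% and 3.1–3.6% across simulations).
- Power is 76.3%, 70.8% and 64.5% plain, against 78.1%, 77.1% and 79.6% by region: losses of 1.9, 6.3 and 15.1 points.

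A check with 20,000 trials gave losses of 1.4, 5.3 and 12.2 points with exact balance, and 1.6, 7.1 and 14.4 with thinning. Plain size was 4.5%, 3.3% and 2.2%, and 4.9%, 4.3% and 3.7%. These agree with the figures above within simulation error.

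**Unplanned interventions (count).** Assume an ST mean of 0.15 and a treatment rate ratio of 2.2:
- Region rate ratio 1: power 73.2% plain, 73.2% by region.
- Region rate ratio 2: 79.9% against 80.8%, a loss of 0.9 points.
- Region rate ratio 3: 83.1% against 86.3%, a loss of 3.2 points; size 4.1% against 4.9%.

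With an ST mean of 0.1, a region ratio of 2 gives 63.7% against 64.9%.

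**Adding centre.** Crossing region with 20 assumed centres makes 40 strata, about 202/40 ≈ 5 patients each. With assumed centre SD 0.5 and δ = 0.5 SD (1,500 trials), stratifying brought size from 3.3% to 4.7%, but power was 69.7% against 69.4% for the plain test.

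**The case against.** The strongest reply is that this is an efficiency preference. The planned test does not inflate type I error, these endpoints carry no decision rule, and the primary non-inferiority claim is untouched. All of that stands and sets the severity.

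The harm is also conditional. The documents give no regional figures for surgery time, closure time, stay or interventions; the leak rates in Protocol 1.1 are indirect evidence. At 0.5 SD the loss is about 1 point, and it becomes material only from roughly 0.75 to 1 SD. For time in surgery, the clock starts at the first skin cut (SAP 9.2), mostly before treatment is revealed, so a 0.4 SD treatment effect is hard to motivate. That limits what is at stake for that endpoint.

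A reader might infer that the true error rate certainly falls well below 5% and that power is certainly lost on all four comparisons. The documents do not support this. Both effects need region to be prognostic, and the conservatism also needs balance within region among the patients analysed, which exclusion after assignment dilutes. How many patients leave at that stage is not stated. In the extreme case the conservatism is essentially absent at 0.5 SD and mild at 1 SD, although the power loss remains.

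Nor do the continuous-outcome figures carry over to the intervention count, where the loss is only about 1 to 3 points.

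**Conclusion.** The point holds as a low-severity inefficiency. The four comparisons ignore a factor that the design stratifies on and the binary models adjust for, and no reason is given. The planned tests are valid.

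Under the assumed 0.4 SD effect, the power loss on the continuous outcomes is nil without a region effect, about 1 point at 0.5 SD, 5 to 6 points at 1 SD (up to about 7 in the extreme thinning case) and about 12 to 14 points at 1.5 SD. For the count it is about 1 point at a region rate ratio of 2 and 3 points at a ratio of 3. The conservatism is real under exact balance but secondary. Every one of these sizes rests on an assumed region effect; the 1.5 SD row marks the far end of the range and is not a forecast.

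A reader might also infer that full stratification by centre and region is needed to mirror the randomisation. The check does not support that: very small strata remove the power gain.

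**What to change.** In SAP 10.2 and 11 and Protocol 9.4.3 and 9.4.4 (and the matching synopsis text), replace the Wilcoxon rank sum test by a van Elteren test stratified by surgical region alone, for all four endpoints. Do not cross region with individual centres. If only the SAP is changed, record the departure in SAP 7.8, which currently lists none.

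The cost is a short text edit in each place and standard software. No extra data or patients are needed, and there is no material power penalty if region turns out not to matter (79.5% by region against 79.3% plain).
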